4.2 METHOD OF TREATMENT ASSIGNMENT

After written informed consent has been obtained and eligibility established, each patient will be assigned an identification number and be randomized to 2:1:1 to one of the three treatment arms through use of an IxRS (see [Figure 1](#) in Section 3.1).

Permuted-block randomization will be applied to ensure a balanced assignment to each treatment arm. Randomization will be stratified by the following criteria:

- Tumor extended RAS status (RAS mutated or RAS wild-type). Extended RAS mutation is defined as mutations occurring in KRAS and NRAS gene codons 12 and 13 of exon 2; 59 and 61 of exon 3; and 117 and 146 of exon 4
- Time since diagnosis of first metastasis (<18 months vs. ≥18 months)

Once the limit of patients with MSI-high tumors has been reached (approximately 5% of patients; see Section 3.3.3), only patients whose tumors are MSI-stable or MSI-low will be enrolled and randomized.

Once the limit of patients with extended RAS wild type (50%) has been reached (see Section 3.3.3), only patients whose tumors are extended RAS mutant will be enrolled and randomized.

Patients should receive their first dose of study treatment as soon as possible and within 3 days of randomization.

4.3 STUDY TREATMENT

The investigational medicinal products (IMPs) for this study are cobimetinib and atezolizumab.

Regorafenib is an approved treatment for mCRC in this disease setting and can be considered standard of care. Regorafenib is a non-investigational medicinal product (NIMP) in this study unless local regulations require it to be an IMP.

4.3.1 Formulation, Packaging, and Handling

4.3.1.1 Cobimetinib

Cobimetinib will be supplied by the Sponsor as tablets. The 20-mg cobimetinib drug product is a film-coated, white, round, immediate-release tablet. Cobimetinib will be packaged in blister packs. The inactive ingredients in cobimetinib are as follows: lactose monohydrate, microcrystalline cellulose, croscarmellose sodium, and magnesium stearate for the tablet core. The tablet coating consists of polyvinyl alcohol, part hydrolyzed, titanium dioxide, polyethylene glycol 3350, and talc. Cobimetinib should not be stored above 25°C (77°F). If the study drug is stored outside of the permitted temperature ranges, quarantine the affected supply and contact the monitor.

For further details, see the cobimetinib Investigator's Brochure.

4.3.1.2 Atezolizumab

Atezolizumab will be supplied by the Sponsor as sterile liquid in 20-mL glass vials. The vial is designed to deliver 20 mL (1200 mg) of atezolizumab solution, but may contain more than the stated volume to enable delivery of the entire 20 mL volume. Extraction of 14 mL of atezolizumab solution from a 1200 mg per vial contains an

840-mg dose. For information on the formulation and handling of atezolizumab, refer to the Investigator's Brochure and Pharmacy Manual.

4.3.1.3 Regorafenib (Stivarga®)

The control arm (Arm C) is regorafenib. In countries where regorafenib is considered an NIMP by local regulations and is commercially available, the commercial formulation of regorafenib (Stivarga) will be provided by the local institution as part of standard of care treatment. It will be provided or reimbursed by the Sponsor if it is considered an IMP by local regulations (see Section 4.3.3) or not commercially available.

For information on the formulation, packaging, and handling of regorafenib, see the Stivarga (regorafenib) Prescribing Information.

4.3.2 Dosage, Administration, and Compliance

4.3.2.1 Cobimetinib

Patients randomized to cobimetinib will receive 60 mg (three tablets of 20 mg each) orally once daily for Days 1–21 of a 28-day cycle as stated in Section 3.1, including Figure 2. This 4-week period is considered a treatment cycle.

Cobimetinib should be taken at the same time every day. It can be taken with or without food. If a dose of cobimetinib is missed or if vomiting occurs when the dose is taken, resume dosing with the next scheduled dose.

Guidelines for dosage modification and treatment interruption or discontinuation are provided in Section 5.1.4.

Any overdose or incorrect administration of study drug should be noted on the Study Drug Administration electronic Case Report Form (eCRF). Adverse events associated with an overdose or incorrect administration of study drug should be recorded on the Adverse Event eCRF (See Section 5.3).

4.3.2.2 Atezolizumab

Atezolizumab dose and schedule will depend on the treatment arm:

- Arm A: cobimetinib plus atezolizumab 840 mg IV q2w
- Arm B: atezolizumab 1200 mg IV q3w as monotherapy

Both dosing schedules will be administered in a monitored setting where there is immediate access to trained personnel and adequate equipment/medicine to manage potentially serious reactions.

For more detailed information on drug preparation, storage, and administration, refer to the Investigator's Brochure and Pharmacy Manual.

Atezolizumab infusions will be administered per the instructions outlined in Table 1.

Table 1 Administration of First and Subsequent Infusions of Atezolizumab

First Infusion	Subsequent Infusions
Premedication is allowed.	If patient experienced IRR during any previous infusion, pre-medication with antihistamines may be administered for Cycles ≥ 2 at the discretion of the treating physician.
Record vital signs (HR, RR, BP, and T) within 60 min before starting infusion.	Record patient's vital signs (HR, RR, BP, and T) within 60 min before starting infusion.
Infuse atezolizumab (one vial in 250 mL NaCl) over 60 (± 15) min	If the patient tolerated the first infusion well without infusion-associated AEs, the second infusion may be delivered over 30 (± 10) min.
Record vital signs (HR, RR, BP, and T) during the infusion or after the infusion if clinically indicated	If the patient had an IRR during the previous infusion, the subsequent infusion must be delivered over 60 (± 15) min.
Patients will be informed about the possibility of delayed post-infusion symptoms and instructed to contact their study physician if they develop such symptoms.	Record patient's vital signs (HR, RR, BP, and T) during the infusion or after the infusion if clinically indicated or patient experienced symptoms during the previous infusion. If no reaction occurs, continue subsequent infusions over 30 (± 10) min with same schedule for recording vital signs.

AE = adverse event; BP = blood pressure; HR = heart rate; IRR = infusion-related reaction; NaCl = sodium chloride; RR = respiratory rate; T = temperature.

Dose modifications to atezolizumab are not permitted. Guidelines for treatment interruption or discontinuation and the management of specific adverse events associated with cobimetinib and atezolizumab are provided in Section 5.1.4 and Appendix 3. For information regarding management of atezolizumab-associated adverse events, please refer to Appendix 9.

For anaphylaxis precautions, see Appendix 4.

See the Pharmacy Manual for detailed instructions on drug preparation, storage, and administration.

Any overdose or incorrect administration of study drug should be noted on the Study Drug Administration eCRF. Adverse events associated with an overdose or incorrect administration of study drug should be recorded on the Adverse Event eCRF (See Section 5.3).

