The schedule of study assessments and procedures are detailed in [Appendix 1](#). After signing informed consent, patients will undergo screening procedures that include testing the tumor for extended RAS mutation status and MSI status (local tests accepted but confirmatory centralized testing required); laboratory tests (e.g., hematology, chemistries, liver function tests); left-ventricular function evaluation (echocardiogram [ECHO] or multigated acquisition scan [MUGA]); contrast-enhanced computed tomography (CT) scan or magnetic resonance imaging (MRI) of the chest, abdomen, and pelvis; and ophthalmologic assessments.

All eligible patients will be randomized to treatment in either Arm A (cobimetinib plus atezolizumab), Arm B (atezolizumab monotherapy) or Arm C (regorafenib). The dosing regimen and schedule for each treatment arm is shown in [Figure 2](#) and Section [4.3](#).

All patients will be closely monitored for safety and tolerability during all cycles of therapy, at the treatment discontinuation visit, and during the follow-up period. The NCI CTCAE v4.0 will be used to characterize the toxicity profile of the study treatments on all patients.

Patients will be assessed for adverse events according to the schedule of assessments in [Appendix 1](#) and as necessary throughout the study.

[figure not shown]
Tumor response will be evaluated according to RECIST v1.1 (see [Appendix 5](#)). Any evaluable and measurable disease must be documented at screening and re-assessed at each subsequent tumor evaluation. Investigators will assess tumor response at 8-week intervals, regardless of any dose delays or treatment cycle.

Treatment will continue until the patient has disease progression according to RECIST v1.1, unacceptable toxicity, death, patient or physician decision to withdraw, or pregnancy, whichever occurs first. A rising CEA level alone is not considered disease progression. No crossover will be allowed. Patients are allowed to receive study treatment beyond disease progression if certain conditions are met ([Section 4.3.2.4](#)).

After discontinuation of study treatment, patients may receive any subsequent line therapy as directed by their treating physician.

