4.5.4 Vital Signs

Vital signs are defined as: temperature (°C), heart rate, respiratory rate, and systolic and diastolic blood pressure. Height and weight will be recorded on Cycle 1 Day 1.

4.5.4.1 Vital Signs for Patients Assigned to Receive Atezolizumab with or without Cobimetinib (Arms A and B)

Vital signs will be measured and recorded at the following timepoints:

- Within 60 minutes prior to infusion
- During infusion and/or after infusion if clinically indicated

For patients in the atezolizumab arm who experienced an infusion-related reaction during the previous atezolizumab infusion, refer to Section [5.1.4](#).

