5.1.4.4 Management of Adverse Events in the Atezolizumab Monotherapy Arm (Arm B)

Guidelines for management of patients who experience specific adverse events associated with atezolizumab, including infusion-related reactions and immune-related events (e.g., pulmonary, hepatic, gastrointestinal, endocrine, ocular, pancreatic, dermatologic, and neurologic events), are provided in [Appendix 9](#).

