Appendix 1 Schedule of Assessments (cont.)

- ^s PRO instruments EORTC QLQ-C30 and EQ-5D-5L will be completed in this order using an electronic device on Day 1 of each cycle during a visit and prior to any assessments. Data will be collected at end of study and at survival follow-up at 3 and 6 months only. In the event a study visit is conducted by telephone, the PRO data for that visit will be collected via telephone interview and recorded by the investigative staff on the ePRO tablet. To maintain validity and minimize patient burden, the PRO instruments administered via telephone interview will consist of a reduced version of the EORTC QLQ items (Items 1–7, 10, 12, 13, 16, 17, 18, 29, and 30 from the C30 and the two additional items from the item bank) and the telephone interview version of the EQ-5D-5L.
- ^t The initial dose will be delivered over 60 (\pm 10) minutes. If the first infusion is well tolerated all subsequent infusions will be delivered over 30 (\pm 10) minutes until loss of clinical benefit. Dose can be given \pm 7 days from scheduled Day 1 of each cycle.
- ^u Cobimetinib 60 mg/day PO will be given in a 21/7 dosing schedule. Dose can be given \pm 7 days from scheduled Day 1 of each cycle, but the scheduled 7–day break must be \geq 5 days.

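### Appendix 1 footnotes t and s omit Table 1's infusion-reaction exception, so a patient who reacts after a tolerated first infusion is given 30 rather than 60 minutes for the next one (minor)

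*Protocol*

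**What the plan says.** Section 4.3.2.2 of the protocol names the controlling instruction: "Atezolizumab infusions will be administered per the instructions outlined in Table 1". Table 1 in that section gives these durations:

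- First infusion: 60 (±15) minutes.
- Second infusion, if the first was tolerated: 30 (±10) minutes is allowed.
- After a reaction: "If the patient had an IRR during the previous infusion, the subsequent infusion must be delivered over 60" (±15) minutes. This refers to the previous infusion, whichever one that was.
- Otherwise: "If no reaction occurs, continue subsequent infusions over 30" (±10) minutes.

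The atezolizumab administration rows of the Appendix 1 schedules carry their own infusion times, in footnote t for Arm A and footnote s for Arm B. After stating 60 (±10) minutes for the initial dose, both say: "If the first infusion is well tolerated all subsequent infusions will be delivered over 30" (±10) minutes, continuing until clinical benefit is lost. Neither mentions a later reaction and neither refers to Table 1. SAP Appendix 2 reproduces both footnotes.

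**The concern.** The two places apply different tests. Table 1 looks at the most recent infusion; the footnotes look only at the first. They agree as long as nobody reacts after the first infusion, and they part when someone does. The footnotes cannot easily be read as a loose summary, because they cover all later infusions without qualification.

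The footnotes attach to the row that tells site staff when to give atezolizumab, so they supply a usable infusion time at the point of use. A site working from the schedule alone would give a patient who has just reacted a faster infusion than Table 1 permits, and would breach a mandatory instruction in Section 4.3.2.2. The error is therefore in the less safe direction. It is a matter of drug administration and does not bear on the efficacy analysis.

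**Working it through.** No figure in the plan needs reproducing. The check sets the two instructions side by side and then looks for any other text that supplies the missing exception.

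**Inputs.** Table 1 (Section 4.3.2.2): 60 ± 15 minutes after an IRR. Appendix 1 footnotes t and s: 30 ± 10 minutes. Doses (Section 4.3.2.2): 840 mg in Arm A, 1200 mg in Arm B.

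**Windows for the infusion after a reaction, first infusion tolerated**

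| Source | Calculation | Window |
|---|---|---|
| Table 1 | 60 − 15 to 60 + 15 | 45–75 min |
| Footnotes t and s | 30 − 10 to 30 + 10 | 20–40 min |

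Overlap: none. Gap: 45 − 40 = 5 minutes. No single infusion time satisfies both.

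**Ratio of infusion rates, footnote over Table 1.** For a fixed dose this is the inverse ratio of the durations:

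- nominal: 60/30 = 2
- closest permitted times: 45/40 = 1.125
- furthest permitted times: 75/20 = 3.75

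**Permitted rates (dose divided by duration)**

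| Arm | Table 1 after an IRR | Footnote |
|---|---|---|
| A, 840 mg | 840/75 = 11.2 to 840/45 = 18.7 mg/min | 840/40 = 21.0 to 840/20 = 42.0 mg/min |
| B, 1200 mg | 1200/75 = 16.0 to 1200/45 = 26.7 mg/min | 1200/40 = 30.0 to 1200/20 = 60.0 mg/min |

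**When it can first arise.** Arm A is infused on Days 1 and 15 of each cycle. A reaction at Cycle 1 Day 15 affects the infusion at Cycle 2 Day 1. Arm B is infused on Day 1 only. A reaction at Cycle 2 Day 1 affects Cycle 3 Day 1.

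**When it does not arise.** If the first infusion itself causes the reaction, the footnotes' condition fails and they say nothing, so there is no contradiction. Grade 3 or 4 reactions lead to permanent discontinuation in Appendix 9, Table 7, subject to an approved rechallenge; the reaction guidelines in that table are stated for Cycle 1.

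**Does other text restore the exception?**

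- Section 4.5.4.1 has a separate route for patients "who experienced an infusion-related reaction during the previous atezolizumab infusion, refer to Section" 5.1.4. It gives no duration.
- Sections 5.1.4.3 (Arm A) and 5.1.4.4 (Arm B) pass the management of atezolizumab events, "including infusion-related reactions and immune-related events", to Appendix 9.
- Appendix 9, Table 7, sets the rate of the infusion in which the reaction occurs, and for Cycle 1 only. For later infusions its Grade 2 row suggests premedication and close observation, without a duration. Reactions in later cycles are left to institutional guidelines.
- Section 5.1.4.2, Table 4, covers interruption and discontinuation for Grade 3 or 4 toxicities. It sets no infusion time.

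Within these documents, only Table 1 sets the duration of the next infusion after a reaction.

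**The case against.** The best reply is that the governing section already has it right. Section 4.3.2.2 sends infusions to Table 1. Section 3.1 separates the two roles: "The dosing regimen and schedule for each treatment arm is shown in" Figure 2 and Section 4.3, while for Appendix 1 "The schedule of study assessments and procedures are detailed in" that appendix. On this reading the footnotes are a shortened default in a visit grid. This stands as far as it goes: Table 1 should prevail. But no precedence clause says so, and the argument only shows which text to correct.

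Second, harm requires a site to ignore Section 4.3.2.2. Infusions are given in a monitored setting, and the Investigator's Brochure and Pharmacy Manual, to which the protocol refers for administration detail, were not available. Appendix 9, Table 7, also lets a Grade 1 reactor in Cycle 1 return to the original rate during the same infusion once 30 minutes at the reduced rate have been tolerated. These points limit the practical risk, and they support a minor grading. They do not reconcile the two windows.

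Third, nothing in the documents links the rate in mg/min to reaction risk. That is correct. The rates above describe how far apart the instructions are and do not estimate harm.

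Finally, the same footnotes give ±10 minutes for the initial infusion where Table 1 gives ±15. That difference is harmless, since 50–70 minutes lies inside 45–75, but it could be aligned in the same edit.

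**Conclusion.** The inconsistency is real and minor. For a patient who tolerates the first infusion, has a later reaction and continues atezolizumab, Table 1 and the footnotes prescribe windows that cannot both be met, and the footnote's nominal rate is twice that of Table 1. Confidence in the textual conflict is high.

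The practical consequence is less certain. The documents give no count of later reactors, and the group is probably small because first-infusion reactors and most Grade 3–4 reactors fall outside it. The conclusion assumes that the Investigator's Brochure and Pharmacy Manual do not already correct the schedule footnotes for sites. The primary endpoint, error control, power and the timing of the analysis do not depend on this point.

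**What to change.** In protocol Appendix 1, footnotes t and s, replace the second sentence with wording such as:

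*If the first infusion is well tolerated, subsequent infusions are delivered over 30 (±10) min only if no IRR occurred at the previous infusion; after an IRR, 60 (±15) min, per Table 1 (Section 4.3.2.2), until loss of clinical benefit.*

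The explicit reference to Table 1 also settles which text governs. Carry the same wording into the two SAP Appendix 2 copies, for consistency only, since the SAP does not direct drug administration.

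The cost is one clause in each of two protocol footnotes, which can wait for the next amendment, and the same clause in two SAP footnotes at the next SAP revision. Data collection and analysis do not change.

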4.3.2.3 Regorafenib

Regorafenib will be used in the commercially available formulation.

Patients randomized to regorafenib (Arm C), will receive regorafenib at the approved dose level of 160 mg (four tablets of 40 mg each) orally once daily on Days 1–21 of a 28-day cycle (see Section 3.3 and Figure 2 in Section 3.1). This 4-week period is considered a treatment cycle.

Regorafenib should be taken at the same time each day. The tablets should be swallowed whole with water after a light meal that contains <30% fat. An example of a light (low-fat) meal would include one portion of cereal (about 30 g), one glass of skimmed milk, one slice of toast with jam, one glass of apple juice, and one cup of coffee or tea (520 calories, 2 g fat).

The study investigator may implement dose interruption or dose reduction in response to adverse events to ensure patient safety and tolerability. Guidelines for dosage modification and treatment interruption or discontinuation are provided in Section 5.1.4.1. Please refer to the Stivarga (regorafenib) prescribing information for more details.

Any overdose or incorrect administration of regorafenib should be noted on the Regorafenib Administration eCRF. Adverse events associated with an overdose or incorrect administration of regorafenib should be recorded on the Adverse Event eCRF (See Section 5.3).

4.3.2.4 Dosing of Study Treatment Beyond Disease Progression

Dosing of study treatment beyond RECIST v1.1–defined disease progression is allowed for patients on all treatment arms. Patients must meet all of the following criteria to be allowed to receive study treatment beyond disease progression:

- Evidence of clinical benefit as assessed by the investigator
- Absence of symptoms and signs indicating unequivocal progression of disease. Patients may continue to receive treatment beyond disease progression in the absence of clinical signs or symptoms of progression despite a rising CEA level.
- No decline in ECOG performance status that can be attributed to disease progression
- Absence of tumor progression at critical anatomical sites (e.g., leptomeningeal disease) that cannot be managed by protocol–allowed medical interventions
- Patients must provide written consent to acknowledge deferring these treatment options in favor of continuing study treatment at the time of RECIST v1.1-defined disease progression
- Approved by the study Medical Monitor

4.3.3 Investigational Medicinal Product Accountability

The IMPs required for completion of this study (i.e., cobimetinib, atezolizumab, and regorafenib if considered an IMP by local regulations) will be supplied or reimbursed by the Sponsor where required by local health authority regulations. The study site will acknowledge receipt of cobimetinib and atezolizumab using the IxRS to confirm the

shipment condition and content. Any damaged shipments will be replaced. Where regorafenib is supplied by the Sponsor, shipment receipt will be documented using IxRS; otherwise, it will be documented per local practice.

IMPs will either be disposed of at the study site according to the study site's institutional standard operating procedure or returned to the Sponsor with the appropriate documentation. The site's method of IMP destruction must be agreed to by the Sponsor. The site must obtain written authorization from the Sponsor before any IMP is destroyed, and IMP destruction must be documented on the appropriate form.

Accurate records of all IMPs received at, dispensed from, returned to, and disposed of by the study site should be recorded on the Drug Inventory Log.

4.3.4 Post-Trial Access to Cobimetinib and Atezolizumab

The Sponsor will offer post-trial access to the study drugs cobimetinib and atezolizumab free of charge to eligible patients in accordance with the Roche Global Policy on Continued Access to Investigational Medicinal Product, as outlined below. Note that regorafenib will not be offered free of charge after study completion.

A patient will be eligible to receive cobimetinib and atezolizumab after completing the study if all of the following conditions are met:

- The patient has a life-threatening or severe medical condition and requires continued study drug treatment for his or her well-being
- There are no appropriate alternative treatments available to the patient
- The patient and his or her doctor comply with and satisfy any legal or regulatory requirements that apply to them

A patient will not be eligible to receive study drug after completing the study if any of the following conditions are met:

- The study drug is commercially marketed in the patient's country and is reasonably accessible to the patient (e.g., is covered by the patient's insurance or wouldn't otherwise create a financial hardship for the patient)
- The Sponsor has discontinued development of the study drug or data suggest that the study drug is not effective for colorectal cancer
- The Sponsor has reasonable safety concerns regarding the study drug as treatment for CRC
- Provision of study drug is not permitted under the laws and regulations of the patient's country

The Roche Global Policy on Continued Access to Investigational Medicinal Product is available at the following Web site:

http://www.roche.com/policy_continued_access_to_investigational_medicines.pdf

